### ***Type 1 Exclusions***

Type 1 exclusions are exclusions that can be automated and do not require consensus among investigators. A research team member who will not be involved with conducting the primary study analyses will use type 1 exclusions to determine when participant recruitment is complete. Recruitment for the present study will end once 500 participants have been randomized *who pass all type 1 exclusions tests* (i.e. are still eligible for inclusion after excluding for type 1 criteria; see our section on sample size for more details).

Here, we will exclude participants that fail to meet the following study inclusion criteria:

- Must be 13 - 16 years old at the time of the baseline survey
- Must report comfort reading and writing in English

- Must endorse no learning disability, visual impairment, or other difficulty that makes it difficult to answer questions on a computer
- Must have access to a laptop or smartphone with internet access
- Must endorse purposefully hurting self without wanting to die within the past month
- Must endorse *either* “I do not like myself” or “I hate myself” on CDI-II item 7 in a screener survey

Here, we will exclude the following participants based on failure to meet the following quality check criteria:

- Participants who exit the study *prior* to condition randomization for our listed analyses (note: the present study will use an intention-to-treat approach, where every participant who was randomized to a study condition—and who is not excluded for one of the specific reasons outlined in this section—will be included in our analyses)

### **Type 2 Exclusions**

Type 2 exclusions are exclusions that cannot be automated and require consensus among investigators. Participants excluded for type 2 reasons will be subtracted from the N = 500 total individuals who were randomized and met criteria for inclusion following type 1 exclusions.

Here, we will exclude the following participants based on failure to meet the following quality check criteria:

- Participants who respond with either copy/pasted responses from text earlier in the intervention (e.g. copy and pasting only text from a previous testimonial slide) to any of free response questions
- Participants demonstrating an obvious lack of English fluency in open response questions; these participants will be identified by consensus from all study team members
- Participants responding with random text in open response questions; these participants will be identified by consensus from all study team members
- Duplicate responses from the same individual in baseline or follow-up surveys (i.e. more than one response with an identical IP address). Where duplicate responses for the same individual are present in the same survey (e.g. more than 1 response for a single individual at follow-up), we will exclude the response that is less complete, retaining the more complete of the two responses. If both responses are 100% complete, we will retain the first of the two responses for that survey. Notably, if an individual completes the baseline survey more than once—and happens to be randomized to both conditions—we will exclude this individual’s responses from our analysis altogether.
- We will also exclude for primary analyses (but may run sensitivity analyses including them) any participants who provide responses of 3 words or fewer to writing prompts that ask for at least 2 sentences or more.

These exclusions are based on previous single session intervention research conducted online

(for one example, see Schleider & Weisz, 2018:  
<https://doi.org/10.1080/15374416.2017.1405353>)

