### ***Secondary Dependent Variables***

**Likelihood of Future NSSI.** Likelihood of future NSSI will be measured immediately pre- and post-intervention. We will evaluate self-reported likelihood of future non-suicidal self-injury immediately post-intervention—comparing participants in the Project SAVE SSI versus supportive therapy SSI control conditions, and controlling for pre-intervention likelihood score. An item from the Self-Injurious Thoughts and Behaviors Interview-R (Fox et al., 2020) will assess participants’ beliefs about the likelihood of future non-suicidal self injury on a 5-point Likert Scale (range = 0 to 4; 0 = “not at all”; 4 = “extremely”).

**SI Frequency in the Past 3 Months.** We will compare past 3-month SI frequency at 3-month follow-up—for participants assigned to the Project SAVE SSI versus supportive therapy SSI (i.e. control condition). At pre-intervention and 3-month follow-up time points, participants will indicate “how many days did they have thoughts about killing themselves for more than a few minutes” in the past 3 months in an open-response text box. Notably, in the present study’s survey flow, this question is displayed following display logic—such that participants endorsing zero history of SI in the past 3 months (via a previous question) skip to the end of the question block and are not prompted to answer our frequency outcome question. For these individuals, we will impute a past 3-month frequency value equal to 0 (as they have endorsed zero SI in the previous 3 months in the earlier question). More information about how we will handle very large numbers (i.e. outliers) for this outcome is reported below (see “Outliers and Exclusions” section; “Winsorizing Outliers” subsection).

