#### **How many and which conditions will participants be assigned to? (optional)**

Participants will be randomly assigned to 1 of 2 possible conditions, per a 1:1 allocation ratio: (1) an online, active control group program encouraging feelings disclosure (i.e. supportive therapy SSI), or (2) an online program targeting behaviors and thoughts relating to self-injury (i.e. Project “SAVE”—Stop Adolescent Violence Everywhere—SSI). Random assignment to condition will be conducted in a triple-masked manner. Therefore, participants will be masked to whether they received active treatment and investigators will be masked to which condition the participant is randomized to—as the randomization occurs automatically within the survey. Additionally, as the primary and secondary outcomes are self-report measures, we will not be utilizing an outcomes assessor (e.g. a clinical interviewer). Participants will be informed of their condition assignment following their completion of the full study protocol by debriefing form. Investigators will be informed of participant condition after data collection is complete (i.e. the data analysis phase).

**Supportive Therapy (“Share Your Feelings”) SSI** (Schleider & Weisz, 2019; see <https://osf.io/u4axs/>) is a ~30-minute, self-administered, web-based program that uses components of supportive therapy to encourage feelings sharing. Like Project SAVE, this SSI takes approximately 30 minutes to complete and is self-administered online. The supportive therapy SSI encourages participants in the control group to identify and express their feelings by (1) explaining why sharing feelings is natural, important, and helpful and (2) including testimonials from teens who have shared their feelings with close others.

**Project SAVE (“Stop Adolescent Violence Everywhere”) SSI** is a ~30-minute, self-administered, web-based program that uses components of cognitive behavior therapy and dialectical behavior therapy designed to decrease self-injurious behaviors in youth. The SSI’s content is designed to maximize relevance for youth engaging in self-injurious behaviors by

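### For repeat baseline entries in the same arm, the duplicate rule can keep a later record whose pre-intervention likelihood of NSSI was answered after program exposure

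*Combined protocol and SAP*

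**What the plan says.** Type 2 Exclusions covers "Duplicate responses from the same individual in baseline or follow-up surveys (i.e. more than one response with an identical IP address"). Between two entries in the same survey, the instruction is: "we will exclude the response that is less complete, retaining the more complete of the two responses". It adds: "If both responses are 100% complete, we will retain the first of the two responses for that survey". Anyone who repeats the baseline survey and "happens to be randomized to both conditions" is removed altogether, so only same-arm repeats remain. The section has no rule for two equally complete entries below 100%.

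Other sections bear on this:

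- The section on conditions explains masking "as the randomization occurs automatically within the survey". No block on re-entry is described.
- Type 1 Exclusions removes people who leave prior "to condition randomization for our listed analyses". It adopts intention-to-treat for "every participant who was randomized to a study condition", subject to the listed exclusions.
- Secondary Dependent Variables states: "Likelihood of future NSSI will be measured immediately pre- and post-intervention". Testing Hypothesis 1 uses the pre-intervention value as the covariate.
- Testing for Differential Dropout and Treatment Effects Among SSI Completers both depend on who counts as having finished.

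Nothing in the plan requires pre-intervention values to come from the first randomized record, and no sensitivity analysis is tied to this rule.

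**The concern.** A baseline covariate should be fixed before the treatment can act on it. How complete a record is becomes known only after randomization, so using it to choose between a person's two randomized records lets later behaviour decide which baseline is analysed. If the first attempt reached program content, the retained baseline may already contain part of the program's effect. Adjusting for it then removes part of the between-arm difference that Hypothesis 1 is meant to estimate.

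There is a second consequence. Someone who stopped after first assignment but finished on a restart is recorded as finishing. That feeds the post-intervention dropout test, whose p-value decides whether the percentile-based sensitivity analysis is run. It also feeds the exploratory completer analysis of the primary outcome. The person stays in the assigned arm, but the point from which they are followed moves from first randomization to a later start.

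**Working it through.** **Plan's own figures.** The only figure to check is 500 randomized, 250 per condition (500 / 2 = 250). The plan gives no repeat rate, effect size, SD or power, and no data had been collected.

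**Step 1: apply the rule to same-arm pairs** (first % complete, second % complete).

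- (100, 100), (100, 60), (70, 40): first kept.
- (60, 100), (40, 70): second kept.
- (60, 60): no rule.

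The second record is kept only when the first was incomplete and the later one went further. Its baseline is post-exposure only if the first attempt had passed randomization and reached program content.

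**Step 2: share of affected records.** Assumed inputs:

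- d, share of participants with two randomized baseline entries: 1% to 10%.
- Probability that the second allocation matches the first: 0.5, from the 1:1 ratio if the draws are independent.
- q, share of same-arm pairs whose later record is the fuller: 0.25 to 1.0. To be cautious, all of these are taken to have had exposure.

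Opposite-arm repeaters leave the analysis, so the share is c = 0.5dq / (1 − 0.5d).

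- d = 1%, q = 0.25: 0.625 of 497.5 records, c = 0.13%.
- d = 5%, q = 0.5: 6.25 of 487.5, c = 1.28%.
- d = 10%, q = 1: 25 of 475, c = 5.26%.

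**Step 3: effect on Hypothesis 1.** Suppose the retained baseline carries the full between-arm effect and the second run adds nothing. The estimate is then about effect × (1 − slope × c). With an assumed slope of 0.5 to 0.9:

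- Smallest loss: 0.5 × 0.126% = 0.06%.
- Middle: 0.7 × 1.28% = 0.90%.
- Largest: 0.9 × 5.26% = 4.7%.

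On the 0 to 4 item, an assumed effect of −0.30 with slope 0.8 and c = 5% gives −0.30 × (1 − 0.04) = −0.288. If the second run adds a fraction k of the effect, the loss becomes c × (slope − k). With k = 0.5 that is 5% × 0.3 = 1.5%, and with k equal to the slope it is zero.

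**Step 4: simulation check** (250 per arm, effect −0.25 SD, correlation 0.7, 3,000 runs, unadjusted two-sided 5% test). For c = 0, 1.25%, 2.5% and 5%, the mean estimates were −0.251, −0.246, −0.246 and −0.242. The formula at c = 5% gives −0.25 × (1 − 0.035) = −0.241. Power stayed between 0.967 and 0.975.

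**Step 5: other outcomes.** Hypotheses 2 and 3 adjust for retrospective 3-month counts. A program of about 30 minutes can hardly change such a count if the restart follows soon after. The plan gives no interval between repeats.

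**The case against.** The strongest case against is that this is a narrow wording gap with a small, conservative effect.

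- **Size.** With opposite-arm repeaters removed, c = 5% needs d of about 9.5% even at q = 1 (0.5d = 0.05 / 1.05), and c = 10% needs about 18% (0.5d = 0.10 / 1.10). Nothing in the plan suggests such rates. If SAVE works, the bias is toward no effect, so it would not create a false success. This stands.
- **Exposure.** Two fully complete records already resolve to the first. What remains is mainly partial exposure, plus people who finished the program but abandoned the post-intervention questions. The full-effect assumption in Step 3 is therefore an upper case. This stands.
- **Intention-to-treat.** No one is moved between arms and no same-arm repeater is dropped. This stands as a limit: the start point shifts, but the allocation does not.
- **Remedy.** Setting aside an observed second-run post-intervention value in favour of an imputed one is a trade-off, and the plan itself warns that imputing from completers may miss what happened to dropouts. This stands for the outcome value. It does not apply to the baseline values, which the first record normally already holds.

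A reader might also infer more than the plan supports: that the second attempt is usually the one kept, that the retained baselines were in fact recorded after exposure, or that only the SAVE arm is affected. The plan says nothing about which attempt tends to be fuller, exposure depends on how far the first attempt went, and the control is itself an active program that could shift the item.

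**Conclusion.** The point holds in a limited form. For same-arm repeats in which a randomized first attempt reached program content and a later one went further, the rule puts a possibly post-exposure value in the Hypothesis 1 covariate. It can also record the person as a completer despite stopping at first assignment.

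Under the assumed ranges, 0.13% to 5.3% of records would be affected and the Hypothesis 1 effect attenuated by 0.06% to 4.7%, with zero possible depending on what the second run adds. These figures rest on an assumed repeat rate, independent re-randomization and an assumed slope. A reader might infer that the primary result is at risk, but the retrospective counts in Hypotheses 2 and 3 leave them essentially unaffected through their covariates. Severity is low: the case for change is that the rule is wrong in principle and cheap to correct before data exist.

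**What to change.** Amend the duplicate rule in Type 2 Exclusions:

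- For repeat baseline entries by one individual in the same arm, take the allocation, start date and all pre-intervention values from the first randomized record, and link the follow-up response to that record.
- Use completeness only to choose between duplicate follow-up entries.
- For Hypothesis 1, treat a post-intervention likelihood absent from the first record as missing under the planned imputation. Add a sensitivity analysis that uses the second-run value instead.

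This also settles, for baseline entries, the tie below 100% that now has no rule. The cost is a few sentences of text, slightly more missing post-intervention likelihood data, and one extra sensitivity analysis.

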**Specify exactly which analyses you will conduct to examine the main question/hypothesis. (optional)**

***Testing for Differential Dropout***

First, we will test for differential dropout by study condition. To do this, we will use Z-tests of differential proportions where we compare the proportion of people who drop out before completing the study (Y or N) as a function of treatment condition (0 = control group SSI, 1 = Project SAVE SSI). We will run two tests evaluating differential dropout: (1) measuring dropout prior to finishing our post-intervention questions, and (2) measuring dropout prior to finishing our 3-month follow-up questions. To be considered a study “completer” for the post-intervention questions, a participant must have made it through all post-intervention survey sections (i.e. all sections but “final block” section that presents information for study logistics). To be considered a study “completer” for the 3-month follow-up questions, a participant must have made it through all follow-up survey sections (i.e. all sections but “final block” section that presents information for study logistics).

If the *p* value is greater than .05 we will assume dropout was not dependent on condition assignment and can proceed with interpreting the effects of intervention assignment (i.e. proceed with the between-group analyses exactly as described below, starting in the section labeled “Hypothesis 1”).

If the *p* value for this test is less than .05 we will conclude that dropout was dependent on condition assignment, and we will take the following steps to improve the interpretability of our results. Unequal dropout between treatment groups can introduce bias in trial results; however, this is not always the case (Bell, Kenward, Fairclough, & Horton, 2013; <https://doi.org/10.1136/bmj.e8668>). One major concern is that, if data are *not missing at random*, systematic differences may exist between “dropouts” and “completers” that cannot be corrected for, limiting the interpretability of our results. For example, if more control condition participants experienced a worsening of clinical symptoms and dropped out before completing follow-up measures, this worsening of symptoms would not be captured by completers’ data (or by data imputed based on the available completers’ data). Thus, should unequal dropout exist

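### Read literally, the both-conditions exclusion misses a youth who leaves one program and gets further in the other, so that youth is analysed in the arm of the second randomization

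*Combined protocol and SAP*

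**What the plan says.** Under Type 2 Exclusions, duplicates are recognised by "more than one response with an identical IP address". Within one survey the plan resolves them by completeness: "we will exclude the response that is less complete, retaining the more complete of the two responses". It adds: "If both responses are 100% complete, we will retain the first of the two responses for that survey". One exception concerns the arm: "if an individual completes the baseline survey more than once—and happens to be randomized to both conditions—we will exclude this individual’s responses from our analysis".

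Three other places bear on this:

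- The section on conditions says that investigators are masked to assignment, "as the randomization occurs automatically within the survey". A survey left part-way can therefore already carry an arm.
- Type 1 Exclusions states an intention-to-treat approach in which "every participant who was randomized to a study condition—and who is not excluded for one of the specific reasons outlined in this section—will be included". It does not say which assignment counts when one person has two.
- Testing for Differential Dropout defines a completer for the post-intervention questions: "a participant must have made it through all post-intervention survey sections".

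**The concern.** The exception joins two conditions: the baseline survey completed more than once, and randomization to both arms. A youth can meet the second without the first. Leaving a self-administered online program of about 30 minutes and starting again is a plausible way to do so, and the plan itself foresees one person being randomized to both conditions.

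For such a youth the only remaining rule is the one on completeness, which ignores both arm and order of entry. If the later record is fuller, three things follow:

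1. The analysed arm is the one the youth stayed with, not the one first assigned. This feeds into all three confirmatory tests, including the primary NSSI count.
2. For Hypothesis 1, the retained pre-intervention likelihood score (the covariate) was recorded after part of the other program had been seen.
3. The abandoned first attempt no longer counts as a dropout in its own arm, and the youth can reappear as a completer in the other.

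**Working it through.** **Step 1: the rule as a decision table.** The plan has no figure of its own to reproduce here, so the check is of the rule. *Completes* is first read as finishing the survey. That reading has support: the same bullet grades records by completeness and names 100% as a distinct state. Two records belong to one person and lie in opposite arms.

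| First record | Second record | Both completed? | Result |
|---|---|---|---|
| 100% | 100% | yes | person excluded |
| partial | 100% | no | second record kept, second arm |
| partial | longer partial | no | second record kept, second arm |
| 100% | partial | no | first record kept, first arm |
| partial | shorter partial | no | first record kept, first arm |
| partial | equal partial | no | no rule applies |

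Rows 2 and 3 are the problem. Rows 4 and 5 keep the first assignment. Under a loose reading, where *completes* means takes or starts, every row gives exclusion and the problem disappears.

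**Step 2: how many youths.** From the plan: 250 per condition and 1:1 allocation. Assumed, because the documents give no rates: a fraction q quits in each arm, a fraction r of quitters re-enters, the second draw is an independent 1:1, and re-entrants finish.

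Number in the arm opposite to first assignment = 250 × (q_SAVE + q_control) × r / 2.

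With q = 0.20 in both arms, this is 250 × 0.40 × r / 2 = 50r:

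| r | Youths of 500 | Share of each arm | Dilution if effect follows first exposure |
|---|---|---|---|
| 5% | 2.5 | 0.5% | 1% |
| 10% | 5 | 1% | 2% |
| 20% | 10 | 2% | 4% |
| 30% | 15 | 3% | 6% |

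Dilution is the sum of the two arms' shares. It is 0% in every row if the effect follows the program that was finished.

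**Step 3: the dropout test.** Assume 25% quit SAVE, 15% quit control, and r = 20%. First-assigned quitters are 62.5 and 37.5. Re-entrants are 12.5 and 7.5, half of them landing in the other arm: 6.25 from SAVE to control and 3.75 from control to SAVE. The test is the pooled two-proportion Z.

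| Handling | SAVE | Control | z | p |
|---|---|---|---|---|
| Every first attempt counted | 62.5/250 = 25.0% | 37.5/250 = 15.0% | 2.80 | .005 |
| Opposite-arm youths by first randomization; same-arm re-entrants keep the fuller record | 56.25/250 = 22.5% | 33.75/250 = 13.5% | 2.62 | .009 |
| Rule as literally written | 50/247.5 = 20.2% | 30/252.5 = 11.9% | 2.54 | .011 |
| All opposite-arm youths excluded | 50/243.75 = 20.5% | 30/246.25 = 12.2% | 2.49 | .013 |

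The decision at .05 is the same in every row. Of the fall in z from 2.80 to 2.54, 0.18 comes from same-arm re-entry and only 0.08 from the opposite-arm cases.

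**The case against.** The strongest objection is that *baseline survey* is never defined. Imputing Data uses baseline for pre-intervention values. If the term means only the questions before randomization, anyone randomized twice has completed it twice, and the exclusion covers every such youth. This reading is possible but fits less well: the duplicate rule names only baseline and follow-up surveys, which leaves the session and post-intervention questions with no survey to belong to unless they are part of the baseline one. Two readings that place the same youth in different analysis sets are in any case a reason to fix the wording.

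A second objection is that the intent is clear and that Type 2 exclusions are settled by investigator consensus, not by code. The intent probably is to exclude everyone randomized to both arms. But no written rule tells the team to do so here, and the written rule points the other way.

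Three points on size stand in full. The frequency is unknown, and the documents do not say whether re-entry is blocked. The rule keeps the first arm whenever the first record is fuller. Dilution is zero if the effect follows the finished program.

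A reader might infer that the differential-dropout safeguard is compromised. The figures do not support that: in the scenario worked above the decision does not change, and most of the shift comes from same-arm re-entry, which is a separate matter.

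**Conclusion.** The point holds as a gap in the exclusion rule. On the literal and better-fitting reading, a youth randomized to both conditions, whose second record is fuller, is analysed in the arm of the second randomization. That conflicts with the intention-to-treat approach, because behaviour after randomization selects the arm.

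The size is unknown and may be nil. Under assumed rates of 20% quitting and 5% to 30% re-entry it is about 2.5 to 15 of 500 youths, with dilution between 0% and about 6%. Because the movers select themselves, there may also be selection bias, whose direction and size cannot be derived from the documents.

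It would go too far to say that every youth randomized to both arms is misassigned, or that the primary result is materially biased. The documents support neither claim. All of this also presumes that the two records are linked; re-entry from a different IP address would not be detected by the stated method.

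**What to change.** **Minimum change.** In the exception under Type 2 Exclusions, replace the trigger with: *is randomized to both conditions, whether or not either survey was finished*. State that this check comes before the completeness rule. The authors' own exclusion then covers every row of the decision table, including the tie that now has no rule.

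**Preferred addition.** Exclusion still removes people because of what they did after randomization, and it leaves the dropout comparison almost unchanged (20.5% against 12.2% in the scenario above). To respect intention-to-treat, analyse these youths once, in the arm of their first randomization and with that record's pre-intervention values, as the main handling or as a sensitivity analysis. Where this is done, count the abandoned first attempt as a dropout in that arm. This goes beyond the authors' choice to exclude, so they should decide which handling is primary.

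**Cost.** A sentence or two. The survey system should already hold both records and their order of entry. A few complete second-arm records would be lost under exclusion, or their outcomes treated as missing under first-randomization handling.
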